4.5 What are the planned inclusion/exclusion criteria?

Patient Population

The target population is both men and women of any 18 or older with full-thickness tears of the rotator cuff who have failed 6 months of conservative management.

B. Inclusion Criteria

1. Patients who have failed standard non-surgical management of their rotator cuff tear, and who would benefit from a surgical repair of the cuff.

Failed medical management will be defined as persistent pain and disability despite adequate standard non-operative management for 6 months. Medical management will be defined as:

- a) The use of drugs including analgesics and non-steroidal anti-inflammatory drugs
- b) Physiotherapy consisting of stretching, strengthening and local modalities (ultrasound, cryotherapy, etc)
- c) Activity modification

2. Imaging, and intra-operative findings confirming a full thickness tear of the rotator cuff.

C. Exclusion Criteria

Preoperative

1. Characteristics of the cuff tear that render the cuff irreparable: fatty infiltration in the muscles grade III (50%) or greater; superior subluxation of the humeral head; retraction of the cuff to the level of the glenoid rim.
2. Partial thickness cuff tears.
3. Significant shoulder comorbidities e.g. Bankart lesion, osteoarthritis
4. Previous surgery on affected shoulder e.g. Previous rotator cuff repair.
5. Patients with active worker's compensation claims
6. Active joint or systemic infection
7. Significant muscle paralysis
8. Rotator cuff tear arthropathy
9. Charcot's arthropathy
10. Significant medical comorbidity that could alter the effectiveness of the surgical intervention (eg. Cervical radiculopathy, polymyalgia rheumatica)
11. Major medical illness (life expectancy less than 1 year or unacceptably high operative risk)
12. Unable to speak or read English/French
13. Psychiatric illness that precludes informed consent
14. Unwilling to be followed for 24 months
14. Advanced physiologic age

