Various reports have shown that a correlation exists between the anatomical integrity of the cuff as determined by various imaging modalities and the functional outcome following open repair. (5, 6, 14-16) Harryman et al. in a study of 105 patients, demonstrated a 20% re-tear rate by ultrasound in repairs of isolated supraspinatus tendons. In patients with tears involving more than one tendon, over 50% had re-torn. Patients with a healed tear had better function during activities of daily living, greater range of motion and strength compared with patients in whom the cuff had re-torn.(5) Gaziely et al. in a study of 100 patients with surgically repaired full thickness tears found a close correlation between the anatomic integrity by ultrasound and the functional outcome as measured by the Constant score. Patients in whom the repair had not healed had poorer range of motion, strength, and lower activities of daily living outcome.(6) In a study of 30 patients with rotator cuff repairs, post-operative MRI demonstrated recurrent tears in 20% of shoulders. The authors demonstrated a correlation between the anatomical integrity of the tear, and final Constant functional outcome scores and final strength. In patients with non-healed tears, abduction strength never exceeded 4 kg.(14) In a study of 65 patients with an arthroscopically repaired cuff tear by Boileau et al., only 71% of patients had complete healing. The healing rate was even lower (43%) in patients over the age of 65. There was a significant difference in the Constant score and final strength in favour of patients in whom the cuff had healed, as demonstrated by MRI or CT scan.(15) In an earlier study by Galatz et al., 17 of 18 patients who underwent an arthroscopic cuff repair had recurrent tears. At a minimum of two year follow-up, the American Shoulder and Elbow Surgeons (ASES) score was 79.9 points.(16)

Despite recent advances in arthroscopic minimally invasive surgical technique, the re-tear rate following rotator cuff repair remains unacceptably high. Failure of the cuff to heal following repair is associated with poorer functional outcomes and loss of strength with corresponding costs to individuals and society due to loss of productivity and impairment of function. Thus, research into methods to improve healing rates must be sought.

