4.1 THE PROPOSED TRIAL

What is the proposed trial design?

Single center, randomized controlled trial.

Recruitment: Up to 180 consecutive men and women, aged 18 or older with surgical indication for surgical repair of a full-thickness rotator cuff tear consulting one of two Ottawa shoulder surgeons ([name] or [name]). Both surgeons have extensive experience with arthroscopic cuff repair, and are both shoulder fellowship-trained subspecialists. When meeting inclusion and exclusion criteria and providing informed consent, they will be included in this randomized controlled trial. Up to 90 patients will be randomized in blocks of 10 consecutive patients to either a bone trephination group or a soft tissue trephination group. Treatment allocation will be stratified by surgeon. We require a sample size of 90 participants who have been randomized *and* received the intervention, and thus we will need to recruit up to 180 participants, as we have experienced a high percentage (~50%) of participants who were lost to follow up or excluded prior to randomization (reasons include cancelling surgery, not being available for the pre-operative trephination and withdrawing consent).

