4.9 How will the outcome measures be measured at follow-up?

The collection and administration of all outcomes and examinations are standardized and are clearly outlined in the Study Protocol Manual. Surgeons and research assistants will have met on several occasions to discuss and review this protocol.

PRIMARY:

The patients will complete the WORC Score questionnaire pre-operatively and at 3, 6, 12 and 24 months post-operatively. The research assistant, blinded to treatment allocation, will be available to answer any questions. The patient will be examined by the blinded research assistant in a standardized fashion. The surgeon is the last person to examine the patient.

SECONDARY:

The patients will complete the ASES and Constant Score questionnaire pre-operatively and at 3, 6 12 and 24 months post-operatively. The research assistant will be available to answer any questions. The patient will be examined by a blinded assessor in a standardized fashion. The surgeon is the last person to examine the patient and is blinded to the results of the outcomes.

The interpretation of the high-resolution ultrasound is based on healing status and will be carried out by a trained MSK radiologist. Healing status will be documented at both 6 and 24 months as either completely healed, partially healed, or not healed. For tendons partially healed or not healed, the size of the defect will be compared with the size of the tear pre-operatively.

The quantitative T1-MRI will be interpreted by a trained MSK radiologist.

Analysis of the healing matrix will be carried out as described above.

4.10 What is the proposed sample size and what is the justification for the assumptions underlying the power calculations?

The sample size calculation was based on a scale score of 71.31 and standard deviation of 30.43. The authors are assuming superiority from historical controls. Superiority would be considered a difference of more than 30%, or 21.4 points on the WORC scale, from the expected mean. With alpha at 0.05 and power 0.80, the sample size was determined at 33 per group. With a foreseen dropout rate of 25%, we would therefore seek 45 patients per group.

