4.14 Details of planned analyses

Primary:

Primary analyses involve a comparison of the mean WORC scores with control data from patients who have undergone an arthroscopic cuff repair, without trephination, obtained through our prospective database. This analysis is a two-tailed unpaired t-test to assess whether there is a statistically significant difference between groups for the mean WORC scores at all time points. The 5% significance level is employed. The underlying assumption for the WORC score data is that there is a normal distribution. If the sample distribution is determined to depart from normal, then a Wilcoxon rank sum test will be performed.

Secondary:

Similar analysis will be carried out for the functional outcome scores. The ASES, Constant Score, and U/S healing rates will be analyzed for differences at 24 months. The planned secondary analyses are performed using a 5% significance level. The secondary outcomes will be analyzed using appropriate statistics; t-tests for continuous and chi-square for dichotomous variables.

Interpretation of the MRI data will involve a comparison of the quantitative T1 signal intensity.

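### The re-tear comparison ignores tear extent and age, two strong predictors in the protocol's own background; a pre-specified stratified analysis would be a minor, low-cost improvement to a secondary endpoint

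*Combined protocol and SAP*

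**What the plan says.** Eligibility (4.5): "The target population is both men and women of any 18 or older with full-thickness tears of the rotator cuff". There is no restriction on tear size or number of tendons, except that irreparable cuffs are excluded, judged by fatty infiltration, humeral head subluxation and retraction. There is no numeric upper age. The last exclusion reads "Advanced physiologic age" and is not defined.

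Background (section 2): a series of 105 patients found 20% re-tear on ultrasound after isolated supraspinatus repair. For larger tears: "In patients with tears involving more than one tendon, over 50% had re-torn". In an arthroscopic series of 65 patients, 71% healed completely. By age: "The healing rate was even lower (43%) in patients over the age of 65".

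Allocation (4.1, repeated in 4.3): "Treatment allocation will be stratified by surgeon". No other factor is named.

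Outcome (4.9): ultrasound healing is graded in three levels. For tendons not completely healed, "the size of the defect will be compared with the size of the tear pre-operatively". This is the only stated use of pre-operative tear size in an outcome.

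Analysis (4.14): healing rates at 24 months fall under "t-tests for continuous and chi-square for dichotomous variables", with no covariate or stratum named.

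**The concern.** The protocol identifies two strong predictors of its re-tear endpoint and uses neither in the comparison. With about 45 patients per arm, chance can leave one arm with noticeably more multi-tendon tears or older patients, and the crude difference then moves for reasons unrelated to trephination. The descriptive use of tear size in 4.9 cannot correct this, because it applies only to a subset defined by the outcome.

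Re-tear is a named secondary question in section 4. The protocol also says that re-tear and quality-of-life data will support treatment recommendations, so the re-tear estimate should be as robust as the existing data allow.

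**Working it through.** **The plan's own figure.** The only sample size is for WORC: difference 21.4, SD 30.43, two-sided alpha 0.05, power 0.80. A t-based calculation gives 32.7, so 33 per group as stated. Inflating for 25% dropout gives 33 / 0.75 = 44, against 45 stated. No rate, power or sample size is given for re-tear, so 45 and 33 per arm are both used below.

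**Size of the contrasts (section 2).**
- Tendon number: 50 / 20 = 2.5-fold, a lower bound because the text says over 50%.
- Age: (100 - 43) / (100 - 71) = 57 / 29 = 1.97-fold, over-65s against the whole series.
- Over 65 against 65 or under needs the share f over 65, which is not given. Risk in the younger group = (0.29 - 0.57f) / (1 - f). The ratio is 2.2 at f = 0.10, about 2.5 at f = 0.18 and about 3.4 at f = 0.30.

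**Chance imbalance and its effect.** Assumptions: re-tear 20% and 50%; multi-tendon share q of 30-50% (not in the documents).
- Marginal risk p = 0.20 + 0.30q.
- SD of the between-arm difference in multi-tendon share = sqrt(2q(1 - q)/n).
- Standard error of the crude re-tear difference with no effect = sqrt(2p(1 - p)/n).
- Within-stratum variance as a fraction of the total = (0.16(1 - q) + 0.25q) / (p(1 - p)).

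| q | p | SD of imbalance, n = 45 / 33 | SE of crude difference, n = 45 / 33 | Variance fraction |
|---|---|---|---|---|
| 0.3 | 0.29 | 0.097 / 0.113 | 0.096 / 0.112 | 0.908 |
| 0.4 | 0.32 | 0.103 / 0.121 | 0.098 / 0.115 | 0.901 |
| 0.5 | 0.35 | 0.105 / 0.123 | 0.101 / 0.117 | 0.901 |

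A 10-point imbalance shifts the crude difference by 0.10 x 0.30 = 3 points, about 0.3 of a standard error. From exact binomial probabilities, an imbalance of 10 points or more has probability 0.30-0.34 at 45 per arm and 0.35-0.39 at 33. For 15 points or more the figures are 0.13-0.17 and 0.23-0.27.

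**Does stratifying help?** Simulation under the same assumptions (40,000 runs per setting), crude chi-square against a Cochran-Mantel-Haenszel test by tendon number:
- Type I error overall: 5.1-5.7% crude, 4.8-5.0% stratified.
- Type I error when imbalance is 15 points or more: 7.1-8.5% crude, about 5% stratified.
- Power for a halved re-tear risk, 45 per arm: 0.40-0.49 crude, 0.40-0.50 stratified.
- The same, when the better arm carries the 15-point excess of multi-tendon tears: 0.22-0.32 crude, 0.39-0.50 stratified.

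**Precision of the estimate.** With no effect, the square root of the variance fraction is 0.949-0.953, a reduction of about 5% in the standard deviation. Simulating the Mantel-Haenszel risk difference itself (200,000 runs per setting, 33 and 45 per arm) gives reductions of 4.1-4.7% with no effect and 2.7-3.1% with a halved risk.

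**The case against.** The strongest reply is that this is a preference for covariate adjustment on a secondary endpoint that was never powered. Randomisation protects the crude test on average, its standard error already includes the variation in case mix, and overall type I error is close to nominal. All of that stands.

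A reader might infer that the 8-10% reduction in variance (7.5% if the multi-tendon share is 20%) equals about 10% more patients. The simulation does not bear this out: average power is virtually the same with and without stratification.

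A reader might also infer a 2.5-fold contrast for both factors, or entry at any adult age. The documents support 2.5-fold for tendon number only. The age contrast is about 2-fold against a whole series, and an age-related exclusion exists, though undefined. The tendon figures come from a passage on open repair, and the irreparability exclusions remove some of the worst tears, so the contrast among enrolled patients may be smaller.

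Two practical objections also stand. Tendon count is not listed as a recorded item; the documents establish only eligibility imaging and a pre-operative tear size. And 4.9 grades healing in three levels without saying how the partial grade enters a two-category comparison, which any chi-square or risk difference needs.

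What the reply does not answer is the allocation actually obtained. If imbalance is large, the crude result is hard to interpret, and an adjustment chosen after seeing it is open to challenge.

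**Conclusion.** The point holds as a minor one. The plan leaves two documented predictors out of the re-tear comparison. The cost is a small loss of precision (about 3-5% in the standard deviation of the estimate) and exposure to occasional large chance imbalance. The benefit of stratifying is protection in that case, not more power.

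These sizes rest on the assumed 30-50% multi-tendon share and on the 20% and 50% rates carrying over to arthroscopic repair. The gain from adding age was not quantified, because the share over 65 is not given.

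A reader might infer systematic bias in the trial's re-tear result. The documents do not support that for the randomised comparison asked in secondary question 2, where imbalance arises only by chance. It would be a different matter if healing were compared with the database controls that 4.14 uses for the primary analysis. Section 4.14 does not say which groups the healing comparison uses, so the revised text should name the two randomised arms.

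**What to change.** In 4.14, pre-specify one analysis of ultrasound re-tear between the two randomised arms: a Mantel-Haenszel risk difference with its confidence interval, stratified by pre-operative tear extent and age.

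- Tear extent: one tendon against more than one, read from the eligibility imaging and recorded before allocation, not taken from the intra-operative findings. If tendon count is not recorded, use pre-operative tear size with a cut-point fixed in advance.
- Age: 65 or under against over 65, the split used in the background series.
- State how the three healing grades form the two categories.
- Report the crude chi-square as a sensitivity analysis, and show both factors by arm at baseline.
- Leave eligibility and stratification by surgeon as they are.

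The cost is a few lines of analysis-plan text, an explicit field for tear extent and minor programming. No extra patients or visits are needed. The downsides are that both factors and their cut-points must be fixed in advance, and that some of the four strata will be small.

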4.6 What is the proposed duration of treatment period?

The insertion site preparation procedure is approximately 15 minutes in duration in total length. All patients follow the same surgical procedure to repair the cuff 10-14 days following preparation, and the same post-operative protocol and a follow-up period of 24 months following cuff repair.

4.7 What is the proposed frequency and duration of follow-up?

Patients are to be assessed in the clinic by the blinded evaluator at post-operative intervals of 3, 6, and 12 and 24 months post operatively. The primary outcome evaluation occurs at the 24 month evaluation. At each clinical follow up, the patient will be assessed with the clinical outcome measures. It is anticipated that at each clinic visit approximately 20 minutes will be spent with the assessor. However, as in all doctors' clinics, some waiting can be anticipated and this can be variable depending on clinic loads and nature of cases.

Radiographic analysis will be done with a high-resolution ultrasound at 6 and 24 months following surgical repair. An MRI T1 quantitative sequence will be carried out 6 weeks following surgical repair. An independent investigator trained in MSK radiology will perform evaluation of the imaging.

4.8 What are the proposed primary and secondary outcome measures?

PRIMARY:

2) The Western Ontario Rotator Cuff Index (WORC)(40) is a disease specific evaluation that has proven to be an accurate and valid assessment of function after rotator cuff repair. Because it is specific for rotator cuff disease of the shoulder, it is highly sensitive to small but clinically significant changes in patient function.

SECONDARY:

1) The American Shoulder and Elbow Surgeon's (ASES) score is a shoulder specific assessment tool developed by the American Shoulder and Elbow Society for use in all types of shoulder problem(42). It consists of both patient self-assessment and physician assessment. The patient self-evaluation is divided into two sections: pain and activities of daily living (ADL). Pain is recorded on a visual analogue scale and ADL's are recorded on a numeric scale. The overall score is an equal weight of the two sections and produces a score out of 100. The higher the score, the better the outcome. The physician assessment is divided into four segments: range of motion, physical signs, strength and instability. The results of the physician assessment do not provide a score.

Europeans favor the Constant Score(41). It has been validated, and normalized in comparison to disease free patients and places greater emphasis on range of motion and strength The European shoulder society has adopted the Constant Score for functional assessment of the shoulder. The Constant Score records a variety of shoulder measurements including an objective test of strength using a spring loaded measuring device. The Constant Score reflects an overall clinical functional assessment. This instrument is based on a 100-point scoring system calculated from a self-assessment portion that evaluates pain and ability to perform tasks of daily living, and a clinical assessment which tests active range of shoulder motion and strength. The higher the score the better the outcome.

2) High-resolution ultrasound will be used as the primary outcome measure to determine the re-tear rate at 6 and 24 months following repair. Ultrasound was chosen as it has been shown to have a high degree of accuracy for the diagnosis of rotator tears that is equivalent but less expensive than MRI.(44)

3) Further secondary outcomes which will be monitored during the post-operative course include: operative times of the two procedures, complications, and the incidence of revision surgery in each procedure.

4) Quantitative T1 MRI will be used to determine the degree of early healing reaction of both procedures. Additional sequences will be carried out to assess the degree of proteoglycan and collagen within the healing substrate.

5) Samples: X grams of tissue will be harvested at the surgical tendon insertion site with a curette. This will include, in the trephination group, an organized blood clot, and superficial bone removed to prepare the surgery. This tissue will be representative of the cellular and extracellular environment at the time of attachment.

Cell identity at the enthesis:

1. Combination of RT-PCR and immunocytochemistry.

1A. Cell isolation and culture: tissue will then be cut into 2mm pieces and digested with 3 mg/ml collagenase type I and 4 mg/ml dispase to generate single-cell suspensions.

1B. Real time PCR: Single-cell suspension of tendon-derived cell will be used to establish the gene expression profile. For each suspension, total RNA will be isolated (expected yield 20 ng and 70 ng RNA/mg wet weight, consistent with the low cellularity of tendon). The quantity and quality of isolated mRNA will be assessed using a Bioanalyzer available in our Department to measure the ratio of absorbance at 260 nm to 280 nm. Isolated RNA will be diluted to 1 ng/ml and stored at -70oC as aliquots, which will be thawed once only. Complementary DNA (cDNA) will be prepared using SuperScript II (Invitrogen), and primed using random hexamers according to the manufacturer's instructions. Two hundred fifty ng RNA will be used for cDNA preparation. The cDNA will be stored at -20oC until required for quantitative real-time PCR. Specific primers and fluorogenic probes for PCR amplification were chosen to detect gene expression profiles related to tendon, cartilage and bone as already published (Table I). To control against amplification of genomic DNA, primers were chosen, where possible, so that amplicons crossed intron-exon boundaries. The 18S ribosomal RNA gene will be used as an endogenous control to normalize for differences in the amount of total RNA in each sample. PCRs will be performed using the ABI Prism 7700 Sequence Detection System according to the manufacturer's protocol.

Table I. List of genes for expression measurement

Bone: osteopontin (Spp1), bone sialoprotein (Ibsp), alkaline phosphatase (AKP1), OSTEOCALCIN (BGLAP1).

Cartilage: Collagen type II and aggrecan

Tendon: scleraxis (Scx), cartilage oligomeric protein (Comp), Sox9, Runt-related transcription factor (Runx2), tenomodulin (TNMD), Tenascin C, fibronectin, type I collagen.

1C. Immunocytochemistry: Single cell suspensions of tendon-derived cells will be fixed with 4% paraformaldehyde in PBS at 25°C for 20 min and immunostained with primary antibodies for 1 hr at room temperature or overnight at 4°C. An immunoperoxidase assay will then be used to detect the immunoactivity after incubation with a secondary antibody. Presence of stem cells will be associated with immunoreactivity positive for: collagen type I, alpha-smooth muscle actin, Comp, tenascin C, fibronectin and negative for: collagen type II and aggrecan.

2. Colony-forming efficiency: Single-cell suspensions will be cultured in a-MEM supplemented with 20% FBS, 100 mM 2-mercaptoethanol, 100U/ml penicillin and 100mg/ml streptomycin for 8-10 days at 37°C under a 5% CO₂ atmosphere. Cells will be cultured in 25-cm² flask and inspected daily under the microscope for 9 days. At the end of the 9-day period, colonies that had formed from single cells will be visualized using methyl violet staining and counted as an indication of the potential clonogenicity.

3. Extracellular matrix: the unique tendon-specific parallel alignment of collagen fibers is able to reflect polarized light. Goldner's trichrome staining. Sharpey's fibers are condensed collagen fibers that insert into the bone.

4. Indicators of tendon matrix formation: the ratio of collagen types I and III and decorin (expect increases). Glutamate production (produced and released by tenocytes) is increased in tendinosis and can be detected by measuring mRNA and proteins corresponding to glutamate transporters VGluT1 and VGluT2. Excessive glutamate production is associated with changes in extracellular tendon matrix metabolism. Decorin regulates assembly of collagen fibrils and acquisition of biomechanical properties during tendon development.

5. Dynamic equilibrium between synthesis and degradation of the tendon extracellular matrix.

Degradation of the tendon ECM is principally mediated by proteinases of the metalloproteinase group; MMP, ADAM, ADAMTS families. Five members of the MMP family including MMPs 1, 2, 8, 13 and 14, have been associated with activity against fibrillar collagen of the tendon. The ADAM family members may participate in inflammatory processes. The ADAMTS family consists of procollagen propeptidases (ADAMTS-2, -3, AND -14) and aggrecanases (ADAMTS-1, -4, -5, -8, -9, and -15) are implicated in tendon-matrix turnover. Of interest, ADAMTS-4 has been shown to cleave other, nonproteoglycan ECM components such as cartilage oligomeric matrix protein, fibromodulin, and decorin. The tissue inhibitors of metalloproteinases (TIMPs) family contain 4 human gene products that are physiologic inhibitors of metalloproteinases. TIMP-3 is the most potent inhibitor of members of these families. The local balance of metalloproteinases and TIMP proteins is likely to be of importance in the correct maintenance of tendon ECM.

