Given the poor healing rate in surgically treated rotator cuff tears, novel techniques to improve healing rates should be sought. There is accumulating evidence that growth factors and pluripotential stem cells have a positive influence on tendon to bone healing. As the proximal humerus has an autologous source of red marrow and corresponding stem cells, this represents a potential source of such cells for the enhancement of tendon to bone healing. There are several potential benefits to using local, autologous cells in this fashion compared with the use of a scaffold materials and any of the available "carriers"; lower cost, technical ease, and most importantly the availability and recruitment of all growth factors, cytokines and stem cells rather than selecting individual factors in isolation. It is possible that the interplay between various growth factors and cytokines is as important as the presence itself of such individual cells and molecules. As we have demonstrated a significant healing reaction by T1 MRI ten days following surgical reinsertion of the rotator cuff in the rabbit model, it is biologically plausible that stimulating the tendon insertion area or cuff tendon prior to surgical repair will have two benefits. The first is the recruitment of MSC's and associated cytokines and growth factors to the repair site prior to the repair. This may allow for a more vigorous healing response as MSC's are present in greater numbers during healing. Second, by stimulating the bone or the tendon prior to repair, the healing rate may be accelerated leading to a lower re-tear rate. Acceleration of healing may be beneficial as a delay in healing can result in gap formation(37-39), which may in turn lead to fibrosis at the tendon insertion rather than healing with chondrocytes. This provides the rationale for study of adjunctive soft tissue or bone trephination for biologic augmentation of rotator cuff repair. Our primary hypothesis is that adjunctive bone trephination prior to arthroscopic cuff repair will lead to higher quality of life outcomes, as measured by the Western Ontario Rotator Cuff score, than soft tissue trephination. Our secondary hypotheses are that bone trephination will lead to higher functional outcomes, strength, lower re-tear rates, and a greater healing reaction (including recruitment of stem cells, cytokines, and growth factors) than soft tissue trephination.

3. References:

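### The stain pattern linked to stem cells largely restates the protocol's own tendon marker list, so on its own it is not shown to distinguish recruited stem cells from tendon cells

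*Combined protocol and SAP*

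**What the plan says.** Item 5 of the secondary outcomes in Section 4.8 describes tissue curetted from the tendon insertion site at the repair operation, and the assays to be run on it.

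- **Step 1C, immunocytochemistry.** The starting material is described thus: "Single cell suspensions of tendon-derived cells will be fixed with 4% paraformaldehyde". The rule follows: "Presence of stem cells will be associated with immunoreactivity positive for: collagen type I, alpha-smooth muscle actin, Comp, tenascin C, fibronectin". The same sentence goes on to name two markers that must not stain, in these words: "negative for: collagen type II and aggrecan".
- **Step 1B and Table I, real-time PCR.** The primers and probes were "chosen to detect gene expression profiles related to tendon, cartilage and bone as already published". The tendon row reads "Tendon: scleraxis (Scx), cartilage oligomeric protein (Comp), Sox9, Runt-related transcription factor (Runx2), tenomodulin (TNMD), Tenascin C, fibronectin, type I collagen". The cartilage row reads "Cartilage: Collagen type II and aggrecan". There is also a bone row, but no stem-cell row.
- **Step 2, colony-forming efficiency.** Single-cell suspensions are cultured, and the resulting colonies are "visualized using methyl violet staining and counted as an indication of the potential clonogenicity". No number of cells seeded is given.

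These assays bear on the secondary hypotheses at the end of Section 2.1, which predict that bone trephination will produce "a greater healing reaction (including recruitment of stem cells, cytokines, and growth factors) than soft tissue trephination". They also bear on secondary research question 4 in Section 4, which asks what the healing tissue is composed of after each procedure.

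**The concern.** The title and rationale rest on bringing marrow-derived stem cells to the insertion site. Section 2.1, under the heading on restoring an enthesis, describes the cells that gather there early as undifferentiated. Yet the stain meant to indicate them requires four markers that the same protocol files under tendon, and it is applied to cells that the protocol describes as coming from tendon.

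If resident tendon cells in the curetting also meet the rule, the readout reflects tendon content as well as stem cells. A difference between arms, or the lack of one, could then be reported as a finding about recruitment when the stain does not support that. The protocol's sampling description has tissue taken only at the repair, so cells not counted before plating cannot be counted afterwards.

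**Working it through.** The plan states no figure on this point, so there is none to reproduce. The check compares the marker sets.

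**Step 1. The rule against Table I (both in Section 4.8, item 5).**

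| Element of the rule | Required | Table I row |
|---|---|---|
| Collagen I | positive | tendon |
| Comp | positive | tendon |
| Tenascin C | positive | tendon |
| Fibronectin | positive | tendon |
| Alpha-smooth muscle actin | positive | none |
| Collagen II | negative | cartilage |
| Aggrecan | negative | cartilage |

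- Positives on the tendon list: 4/5 = 80%.
- Negatives on the cartilage list: 2/2, and they are the complete list.
- Elements that amount to tendon-positive, cartilage-negative: (4 + 2)/7 = 6/7.

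**Step 2. The reverse direction.** The tendon list has 8 genes and the rule uses 4 of them. Scx, Sox9, Runx2 and TNMD are not used. The two sets together hold 5 + 8 − 4 = 9 distinct markers, so the overlap is 4/9 = 0.44. The rule is a subset of the tendon list plus one outside marker, not a copy of the list.

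**Step 3. What the seventh element decides.** If a tendon cell expresses what Table I lists for tendon and lacks what it lists for cartilage, it meets six elements. It then meets the whole rule only if it also stains for alpha-smooth muscle actin. The documents do not say whether tendon cells do, and do not call that marker specific to stem cells.

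**Step 4. Illustration of sensitivity.** This assumes that the stain is scored as the percentage of cells meeting the rule, which the plan does not state. Let s be the true stem-cell fraction and f the share of non-stem cells that also meet the rule. Then

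apparent fraction = s + (1 − s) × f.

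The documents give neither s nor f. Assume s = 5% in one arm and 10% in the other (true ratio 2.0), with the same f in both:

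| f | Apparent, 5% arm | Apparent, 10% arm | Apparent ratio | True stem cells among rule-positive cells, 5% arm |
|---|---|---|---|---|
| 0 | 5.0% | 10.0% | 2.00 | 100% |
| 10% | 14.5% | 19.0% | 1.31 | 34% |
| 25% | 28.75% | 32.5% | 1.13 | 17% |
| 50% | 52.5% | 55.0% | 1.05 | 10% |
| 90% | 90.5% | 91.0% | 1.01 | 6% |

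For example, at f = 25%: 0.05 + 0.95 × 0.25 = 0.2875; 0.10 + 0.90 × 0.25 = 0.325; 0.325/0.2875 = 1.13; and 0.05/0.2875 = 17%.

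If f differs between arms, a difference can appear with none in s. With s = 5% in both, f = 30% gives 0.05 + 0.95 × 0.30 = 33.5%, and f = 50% gives 0.05 + 0.95 × 0.50 = 52.5%. The documents do not say whether f differs, or in which direction.

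**The case against.** The other side has several good points.

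- **Alpha-smooth muscle actin.** A reader might infer that ordinary tendon cells will be counted as stem cells. The documents do not support that. The marker is required, it is outside the tendon list, and nothing says how a tendon cell stains. Table I is also a list of genes for PCR, not a stated protein profile of a tendon cell. Misclassification is an open risk, not a demonstrated fact.
- **Other assays exist.** A reader might infer that recruitment cannot be tested at all. That goes too far. The colony assay does not use these markers, and the cell-identity work is headed as a joint use of PCR and immunostaining. Scx and TNMD, which are on the tendon list but outside the rule, are measured by PCR. However, the plan does not say how the three results combine to identify stem cells.
- **Direction of bias.** A reader might infer that the stain favours one particular arm. Section 4.8 expects clot and superficial bone in the trephination group, but both arms are trephined, so it does not establish which arm's tissue would differ.
- **Wording and weight.** The plan says only that the pattern is associated with stem cells, and gives no threshold or scoring unit. Question 4 is descriptive. Section 4.14 does not name the tissue outcomes; only its general sentence on tests for secondary outcomes could reach them.
- **Colony denominator.** The assay's heading says efficiency, and Section 4.9 refers to a Study Protocol Manual that is not among the documents. The missing number seeded may be given there, so its absence here does not prove that raw counts would be compared.

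These points limit the claim. They do not supply a marker or a combining rule that makes the stain discriminating.

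**Conclusion.** The point holds in limited form. By the protocol's own lists, six of the seven elements of the rule describe tendon-positive, cartilage-negative cells, and the seventh is not identified as specific to stem cells. The stain alone is therefore not shown to distinguish recruited stem cells from resident tendon cells, and a between-arm difference in it should not be read as a difference in recruitment.

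The marker counts are exact. The practical size is unknown because it depends on f, which the documents do not give. Under the assumed fractions, a true doubling would appear as a ratio anywhere from 2.00 (f = 0) to 1.01 (f = 90%). That range shows sensitivity and is not an estimate for this trial.

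The consequence is confined to the stem-cell part of the secondary hypotheses and to secondary question 4. The primary WORC comparison does not depend on it.

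**What to change.** 1. In Section 4.8, step 1C, relabel the panel as a tendon-lineage phenotype and remove the statement linking it to the presence of stem cells.
2. Name the colony-forming assay as the between-arm readout for clonogenic (stem or progenitor) cells. Count the cells before plating and report colonies per cells seeded, as the heading of that step already implies. Carry this into Section 4.14, which does not mention the tissue outcomes.
3. Report the PCR tendon genes outside the rule, such as Scx and TNMD, alongside the colony result, so that the tendon content of each sample is visible.

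The cost is protocol and laboratory wording plus one cell count per sample before plating. No further patients or visits are needed. The downside is that the immunostain can no longer be reported as stem-cell evidence. The colony assay also has a limit: the protocol presents it only as an indication of potential clonogenicity, so conclusions should be worded in terms of clonogenic cells.
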